7.0 Regulatory and ethical compliance

This study was designed and shall be implemented and reported in accordance with the criteria of the “European Network Centres for Pharmacoepidemiology and Pharmacovigilance (ENCePP) study” and follows the ENCePP Code of Conduct (EMA 2014). Once a final version of the protocol has been agreed and reviewed by the advisory group, this study will be registered with www.encepp.eu.

The OPCRD is approved by the Health Research Authority for clinical research use, and governed by the Anonymised Data Ethics & Protocol Transparency (ADEPT) Committee. We will submit the finalised version of this protocol to ADEPT for approval.

Access to the CPRD for research use follows a similar governance process. We will submit an application and protocol for phase 2 of the study to their Independent Scientific Advisory Committee (ISAC) for approval.

8.0 Data dissemination

It is proposed that initial results be presented in poster and/or oral format at ATS 2019 and ERS/EAACI 2019. One manuscript containing more detailed results and methodology will be submitted to a journal specialising in respiratory medicine.

11.0 Timelines

Action	Timeline
Contract signature	0
Literature search (comorbidity severity) & proposal	4 weeks (completed)
Proposal sign-off	1 week (completed)
Full Protocol delivery	3 weeks
Protocol sign-off	2 weeks – To be determined by Regeneron
Dataset delivery (OPCRD) + ADEPT approval	2 weeks
Phase 1 analyses	3 weeks
Sign-off on key clusters of interest	2 weeks – To be determined by Regeneron
Dataset delivery (CPRD) + ISAC approval	12-26 weeks (direct purchase from CPRD)
Phase 2a analyses	5 weeks
Phase 2b analyses	3 weeks
Final study report	3 weeks
Study report sign-off	2 weeks – To be determined by Regeneron
Conference abstract 1	ATS 2019
Conference abstract 2	ERS/EAACI 2019
Manuscript	6 weeks

13.0 APPENDICES

13.1 Appendix 1: Read code lists for asthma (QOF)

See: 160715_Read codes_QOF asthma_v1.0.xlsx

13.2 Appendix 2: Read code lists for other chronic lower respiratory condition

See: 160513_Read code list_Other chronic respiratory disease Dx_v3.0.xlsx and 160219_Read code list_COPD diagnosis_Broad definition_v0.2.xlsx

13.3 Appendix 3: Read code lists for the comorbidities of interest

Existing code lists

Atopic dermatitis: 160129_Read codes_eczema diagnosis_v1.0.xlsx

Allergic rhinitis: 160120_Rhinitis diagnosis_read_codes_v1.0.xlsx

Nasal polyps: 160614_Read code list_Nasal polyps diagnosis_V1.0.xlsx

Anaphylaxis: 160211_Read codes_anaphylactic reactions_v1.0.xlsx

Code lists to be developed

Chronic rhinosinutis

Urticaria

Allergic conjunctivitis

[figure not shown]
Food allergy

Eosinophilic oesophagitis

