3.0 Study design

3.1 List of comorbidities of interest

The nine T2-type comorbidities of interest are: atopic dermatitis; allergic rhinitis; chronic rhinosinusitis; nasal polyps; urticaria; allergic conjunctivitis; food allergy; eosinophilic oesophagitis; and anaphylaxis.

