5.2 Identifying comorbidities of interest

The nine T2-type comorbidities of interest (atopic dermatitis; allergic rhinitis; chronic rhinosinusitis; nasal polyps; urticaria; allergic conjunctivitis; food allergy; eosinophilic oesophagitis; and anaphylaxis) will be identified by the presence of a Read code for the condition in the patient record. Anaphylaxis will also be identified by the prescription of adrenaline. Appendix 3 lists conditions where there are existing Read code definitions and those which will be developed during the study.

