6.3 CONSORT chart

A CONSORT-type chart, describing the number and proportion of patients retained and excluded at each step of the inclusion/exclusion criteria will be generated for each study phase.

6.4 Demographic and clinical characteristics of patients at index date (phase 1 and 2)

Phase 1: The demographic and clinical characteristics at index date of patients included in the analysis will be tabulated: this will include the number and proportion of patients with each of the comorbidities of interest. For completeness, the number of patients with no comorbidities will also be reported. As it will not be possible to distinguish between inactive and active comorbidity and mild to moderate/severe comorbidity for all comorbidities of interest without linked HES data, this will be reported as the number of patients with active/inactive comorbidity.

Phase 2: A similar set of outputs will be produced for the second phase. In addition, the number and proportion of patients whose comorbidity is inactive, active, mild and

moderate/severe will be tabulated for each comorbidity using the primary care and linked HES data.

Patient characteristics at index date will be reported for the study population using the following conventions:

- Continuous variables will be summarised using descriptive statistics: n (non-missing sample size), percentage of non-missing, mean, standard deviation, median, inter-quartile range (25th and 75th percentile), maximum and minimum.
- For categorical measures, the frequency and percentages (based on the non-missing sample size) of observed levels will be reported.

Comorbidity prevalence will be estimated for each comorbidity cluster by dividing the number of patients in the cluster by the total number of patients eligible for inclusion in the study.

The ratio of observed to expected cases for each comorbidity cluster will be estimated by dividing the observed prevalence of the cluster by the expected prevalence of the cluster (the product of the prevalence of each individual disease in the cluster).

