6.5 Identification and selection of comorbidity clusters (phase 1)

There are over 500 possible combinations of the 9 comorbidities of interest. The prevalence of each combination of comorbidities will be tabulated (including patients with no comorbidities) (see mock table in appendix 8). Clusters will be ranked by prevalence. The ratio of observed cases to expected for each cluster and cumulative proportion of population accounted for at each step will be calculated.

Visualisations of the frequency and age distribution of comorbidity in the asthma population will be produced. A table with the source data will accompany each figure. The first figure will chart the frequency of comorbidities in the study population (see illustrative example in appendix 9). The second figure will chart the mean number of comorbidities in the asthma population by age group and gender (appendix 10).

A small set of key comorbidity clusters will then be selected by consensus for further analysis in phase 2. This will be based on their clinical importance, prevalence, observed/expected ratio and cumulative proportion of population included.

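### Appendix 3 identifies atopic dermatitis and allergic rhinitis with code lists titled for eczema and rhinitis generally, and nothing in the protocol limits them to atopic or allergic codes

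*Protocol*

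**What the plan says.** Section 3.1 sets the scope: "The nine T2-type comorbidities of interest are: atopic dermatitis; allergic rhinitis; chronic rhinosinusitis; nasal polyps", followed by five others. Section 5.2 says that the conditions "will be identified by the presence of a Read code for the condition in the patient record". It gives no time window, and for these two conditions no confirmatory criterion.

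Appendix 3 then names the files. Under existing lists it gives "Atopic dermatitis: 160129_Read codes_eczema diagnosis_v1.0.xlsx" and "Allergic rhinitis: 160120_Rhinitis diagnosis_read_codes_v1.0.xlsx". The other two existing lists, for nasal polyps and anaphylaxis, carry the name of their own condition. The remaining five lists are still to be developed.

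Section 6.4 computes cluster prevalence by "dividing the number of patients in the cluster by the total number of patients eligible for inclusion in the study", and takes the expected prevalence as "the product of the prevalence of each individual disease in the cluster". Section 6.5 uses these results to choose the clusters for Phase 2: "This will be based on their clinical importance, prevalence, observed/expected ratio and cumulative proportion of population included".

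**The concern.** The study rests on a shared type 2 mechanism (Section 1.0), so the two labels are meant to mark atopic and allergic disease. A list that follows its title could also take in eczema that is not atopic and rhinitis that is not allergic. A patient with one such code would count as having a T2 comorbidity.

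The label feeds the single-disease prevalences, the exact-combination table, the observed/expected ratios and, through them, the consensus choice of clusters. It then carries into the Phase 2 severity, resource use and cost models. Allergic rhinitis is described in Section 1.0 as possibly the commonest of these conditions, and Appendix 12 uses this very pair as its example cluster.

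**Working it through.** The protocol states no prevalence, ratio or code-list accuracy, so there is no figure to reproduce. The check has two parts: whether the text restricts the lists anywhere, and what unrestricted lists would do to the protocol's own measures.

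**Is there a restriction elsewhere?**
- Section 5.2 asks only for a Read code.
- Section 5.3 grades activity and severity by consultations and by topical or nasal corticosteroids; neither asks for evidence of atopy. Drugs with several indications are attributed to the nearest recorded diagnosis, which may be the same broad label.
- Section 6.9 has one sensitivity analysis, on length of record.

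None of these restricts the lists.

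**Illustration.** All inputs are assumptions: true prevalence A = 20% (atopic dermatitis) and B = 25% (allergic rhinitis); true ratio 1.5; a share s of coded patients, 0 to 40%, without the named condition. Only these two conditions are modelled.

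True cells: both = 1.5 × 0.20 × 0.25 = 0.075; A only 0.125; B only 0.175; neither 0.625.

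Recorded prevalence A′ = A/(1 − s); false-positive rate fA = (A′ − A)/(1 − A); likewise for B.

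If false positives are unrelated to the other condition, both′ = 0.075 + 0.175·fA + 0.125·fB + 0.625·fA·fB, and the ratio is both′/(A′·B′).

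At s = 30%:
- A′ = 0.20/0.70 = 0.2857 and fA = 0.0857/0.80 = 0.1071
- B′ = 0.25/0.70 = 0.3571 and fB = 0.1071/0.75 = 0.1429
- both′ = 0.0750 + 0.0188 + 0.0179 + 0.0096 = 0.1212
- expected = 0.2857 × 0.3571 = 0.1020
- ratio = 1.19

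Let k be how many times more likely a false positive is in patients who carry the other label, holding the total number of false positives fixed (A's errors added first, then B's):

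| s | A′ | B′ | ratio, k = 1 | k = 2 | k = 3 |
|---|---|---|---|---|---|
| 0% | 20.0% | 25.0% | 1.50 | 1.50 | 1.50 |
| 10% | 22.2% | 27.8% | 1.38 | 1.49 | 1.56 |
| 20% | 25.0% | 31.3% | 1.28 | 1.47 | 1.60 |
| 30% | 28.6% | 35.7% | 1.19 | 1.44 | 1.61 |
| 40% | 33.3% | 41.7% | 1.12 | 1.41 | 1.60 |

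With a true ratio of 1.0 and s = 30%, the recorded ratio stays at 1.00 for k = 1 but becomes 1.27 for k = 2.

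**A second pair.** Take rhinitis with chronic rhinosinusitis, assumed 25% and 5%, true ratio 1.5, s = 30% in rhinitis only. True cells: both 0.01875, rhinosinusitis only 0.03125, neither 0.71875. Added false positives total 0.25/0.70 − 0.25 = 0.1071; the expected value is 0.3571 × 0.05 = 0.01786.
- k = 1: rate in rhinosinusitis 0.1429; both′ = 0.01875 + 0.03125 × 0.1429 = 0.0232; ratio 1.30.
- k = 2: rate 2 × 0.1071/(2 × 0.03125 + 0.71875) = 0.2743; both′ = 0.0273; ratio 1.53.
- k = 4: rate 4 × 0.1071/(4 × 0.03125 + 0.71875) = 0.5079; both′ = 0.0346; ratio 1.94.

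**Exact combinations.** Appendix 8 tabulates mutually exclusive combinations that cumulate to 100%, so contamination moves patients between cells. For the first pair, contaminating A alone at 30% with k = 1 takes A only from 12.5% to 19.2%, both from 7.5% to 9.4%, B only from 17.5% to 15.6%, and neither from 62.5% to 55.8%.

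A cell that contains a contaminated condition can also shrink. Assume prevalences of 20% and 30%, true ratio 1.5, and shares of 10% (eczema) and 30% (rhinitis). Then fA = 0.0222/0.80 = 0.0278 and fB = 0.1286/0.70 = 0.1837. The atopic-dermatitis-only cell goes from 11.0% to (0.110 + 0.59 × 0.0278) × (1 − 0.1837) = 10.3%.

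**Against sampling error.** With about 220,000 Phase 1 patients (Section 6.1), a 20% prevalence has a 95% half-width of 1.96 × √(0.2 × 0.8/220000) = 0.17 percentage points. A 10% non-atopic share moves it by 2.2 points, about 13 times as much.

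**The case against.** The strongest reply is that everything rests on two file titles. The spreadsheets are not in the document, a list called eczema or rhinitis may already leave out the unwanted codes, and Section 5.2 does ask for a code for the named condition. This stands: no contamination has been shown, and s = 0 is a possible answer. What it does not remove is that the only description of the lists is broader than the conditions, and no sentence narrows it.

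Three stronger readings are tempting, and the documents do not support them.
- A reader might infer that observed/expected ratios are always diluted towards 1. That needs false positives unrelated to the other condition; the table and the rhinosinusitis example show that the ratio can hold or rise.
- A reader might infer that every cluster containing these conditions gains prevalence and rank. With exact combinations some cells lose patients, and rank is relative.
- A reader might take the Appendix 13 review as proof that the two conditions were broadened on purpose. Its list does say eczema, with atopic dermatitis as a search synonym, but it keeps allergic rhinitis. Search synonyms do not define cases. Its hand eczema material concerns severity, and its repeat-code and steroid-refractory rules were not adopted in Section 5.3.

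It can also be said that keeping unspecified codes leaves some non-atopic patients in. That is true, and it is why the repeat table with specific codes is needed alongside the pruning.

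**Conclusion.** The point holds as a mismatch between the named conditions and the titles of the lists that define them, for two of the nine comorbidities, with no restriction stated anywhere in the protocol. If the lists are as broad as their titles, the recorded prevalence of these two conditions rises, and exact-combination prevalences and observed/expected ratios are distorted in a direction that cannot be fixed in advance.

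The size cannot be computed from the document. Under the assumed inputs, a non-atopic share of 10% to 40% lifts 20% to between 22.2% and 33.3%, and moves a true ratio of 1.5 to anywhere from 1.12 to 1.61. These figures depend on the assumed prevalences, shares and values of k, and are an illustration only. The large sample does not protect against this, because it is an error of classification.

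**What to change.** Before Phase 1, check both existing lists in Appendix 3. Remove codes for explicitly non-atopic eczema and for explicitly non-allergic or infective rhinitis, and keep unspecified codes in the main definition. State the restriction in Appendix 3; if the lists are already restricted, one sentence there closes that part of the point.

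Then repeat the Phase 1 prevalence and observed/expected table using only explicitly atopic and allergic codes, as a sensitivity analysis, before the Phase 2 clusters are chosen. This shows whether the choice depends on code breadth, and it comes ahead of the 12 to 26 weeks that Section 11.0 allows for CPRD data and approval.

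The cost is a review of two lists, one extra table, and the loss of patients whose only code is explicitly non-atopic or non-allergic. The number lost cannot be stated from the document.

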13.4 Appendix 4: GINA step definition

GINA Step:	Drug Class Groups:
1	SABA or LABA +/- SABA(although discouraged without ICS)
2	Low dose (LD) ICS ¹ +/- SABA or LTRA +/- SABA or THEO +/- SABA or LABA + THEO +/- SABA(although discouraged without ICS) or
3	LD ICS + LABA +/- SABA (adults) / Medium dose (MD) ICS + LABA +/- SABA (children) or MD ICS +/- SABA LD ICS + LTRA +/- SABA or LD ICS + THEO +/- SABA or LD ICS + LABA + LTRA +/- SABA or LD ICS + LABA + THEO +/- SABA or LD ICS + LABA + LTRA + THEO +/- SABA or
4	MD /High dose (HD) ICS + LABA +/- SABA (adults) or HD ICS + LABA +/- SABA (children)
5	MD/HD ICS + LTRA +/- SABA or MD/HD ICS + THEO +/- SABA or MD/HD ICS + omalizumab or ICS + LABA + Maintenance oral steroids +/- SABA or ICS + LTRA + Maintenance oral steroids +/- SABA or ICS + THEO + Maintenance oral steroids +/- SABA or Maintenance oral steroids

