5.0 Study variables and study outcome definitions

5.1 Describing demographic and clinical variables

The demographic and clinical characteristics of interest at index date are: gender, age, smoking status, most recent recorded BMI prior to index date, most recent spirometry recorded prior to index date (PEF, FEV₁, FEV₁/FVC ratio), number with severe asthma, GINA step, Risk Domain Asthma Control and Overall Asthma Control, asthma medications in the year prior to index date, blood eosinophil count.

- Smoking status will be categorised as: never smoked; ex-smoker; or current smoker based on the latest recorded Read code prior to the index date.
- Body Mass Index (BMI) will be calculated from height and weight data if available (weight in kg/height in m²) or taken from the practice recorded BMI value if not.
- The most recently recorded Peak Expiratory Flow (PEF), Forced Expiratory Flow in one second (FEV₁) and Forced Vital Capacity (FVC) will be taken from the practice recorded value. FEV₁/FVC ratio will be calculated using the last recorded of each of these two values. FEV₁% predicted will also be calculated and reported,
- Severe asthma will be defined according to the ERS/ATS guidelines (Chung, Kian Fan, et al. "International ERS/ATS guidelines on definition, evaluation and treatment of severe asthma." European Respiratory Journal (2013): erj02020-2013).
- We will also report the number of patients meeting the definition of severe asthma used in Regeneron RCTs.
- GINA step will be determined by prescribed medication: see Appendix 4. Highest GINA step (1-5) in the year prior to the index date will be reported.
- Risk Domain Asthma Control (RDAC). Controlled asthma will be defined as the absence of the following in the year prior to the index date: (i) an asthma-related A&E attendance, in-patient admission or out-patient department attendance; (ii) an acute course of oral corticosteroids with evidence of a lower respiratory consultation; and (iii) an antibiotic prescribed with evidence of a lower respiratory consultation.

- Overall Asthma Control. Controlled asthma will be defined as the absence of the following aspects of asthma risk during the baseline year: attainment of RDAC and an average daily dose of ≤ 200 mcg salbutamol / ≤ 500 mcg terbutaline.

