6.0 Statistical analysis

6.1 Sample size

Phase 1: Approximately 220000 OPCRDR patients with active asthma will be available for inclusion in this phase. Of these, approximately 85000 have moderate to severe asthma (GINA steps 4 & 5).

Phase 2: Approximately 220000 OPCRDR patients and 440000 CPRDR patients with active asthma will be available for inclusion in this phase (85000 moderate to severe from OPCRDR and 170000 moderate to severe from CPRDR). Approximately 260000 of the CPRDR patients will have linked secondary care data (HES): the HES records are required to identify secondary care service use and costs, and for some measures of disease severity.

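### As printed, Appendix 4 ranks LTRA and theophylline add-ons level with LABA at low ICS dose in adults but above it at medium or high dose, so GINA step depends partly on which add-on was prescribed

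*Protocol*

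**What the plan says.** Section 5.1 makes the step a pure function of prescribing: "GINA step will be determined by prescribed medication: see Appendix 4". It then takes the maximum over a year: "Highest GINA step (1-5) in the year prior to the index date will be reported". The mock table in Appendix 7 gives each of the five steps its own line.

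The relevant entries in Appendix 4 are:

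- **Step 3** contains low-dose ICS plus LABA for adults and medium-dose ICS plus LABA for children. It also lists "LD ICS + LTRA +/- SABA or LD ICS + THEO +/- SABA" and combinations up to "LD ICS + LABA + LTRA + THEO +/- SABA". Medium-dose ICS with no add-on is here too.
- **Step 4** reads "MD /High dose (HD) ICS + LABA +/- SABA (adults) or HD ICS + LABA +/- SABA (children").
- **Step 5** begins "MD/HD ICS + LTRA +/- SABA or MD/HD ICS + THEO +/- SABA or MD/HD ICS + omalizumab". It continues with the maintenance oral steroid regimens, such as "ICS + LABA + Maintenance oral steroids +/- SABA".

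Section 6.1 is the only place where steps are grouped. In OPCRD, "approximately 85000 have moderate to severe asthma (GINA steps 4 & 5"), out of about 220,000. The CPRD counterpart is 170,000 out of 440,000. Section 4.2 sets no age limit, so children are in the study.

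**The concern.** An ordinal measure should order its categories by one rule. At low ICS dose in adults the table treats the three add-on classes as interchangeable. At medium and high dose it puts LTRA and theophylline one step above LABA, in the same row as omalizumab and maintenance oral steroids. Two patients on the same ICS dose with one add-on each can therefore land on different steps because of the add-on alone.

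GINA step is a planned descriptive output. Section 6.6 also compares asthma severity between comorbidity clusters and models disease severity by logistic regression, without naming the severity measure, so GINA step is not ruled out there. If LTRA prescribing differs between clusters, part of any difference in step could reflect drug choice and not severity.

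**Working it through.** No outside guideline is needed. The check sets the entries of Appendix 4 side by side.

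**1. Steps as printed, adults (exact match to a listed regimen)**

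| ICS dose | No add-on | + LABA | + LTRA | + THEO | + LABA + LTRA or THEO |
|---|---|---|---|---|---|
| Low | 2 | 3 | 3 | 3 | 3 |
| Medium | 3 | 4 | 5 | 5 | not listed |
| High | not listed | 4 | 5 | 5 | not listed |

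Within the low-dose row the single add-ons tie. Within the medium and high rows they do not. Medium-dose ICS + LTRA (5) is above high-dose ICS + LABA (4), although the latter has the higher ICS dose and the same number of add-ons.

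**2. Steps as printed, children**

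Only the LABA entries of steps 3 and 4 carry an age label. The LTRA and theophylline entries carry none, so I read them as applying at all ages.

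| ICS dose | + LABA | + LTRA | + THEO |
|---|---|---|---|
| Medium | 3 | 5 | 5 |
| High | 4 | 5 | 5 |

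At medium dose the add-on decides whether a child is outside (3) or inside (5) the step 4–5 group.

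**3. Effect of the highest-step rule**

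Medium-dose ICS alone is step 3. An LTRA added for part of the year meets a step 5 entry, so the recorded step moves from 3 to 5.

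**4. Sensitivity to the row boundary**

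Suppose the LTRA and theophylline entries at the head of row 5 belong at the end of row 4. In adults, medium- or high-dose ICS plus any one of the three add-ons is then step 4, and the inversion disappears. In children, medium-dose ICS + LABA is still 3 while + LTRA or THEO becomes 4, so the pooled group still depends on the add-on.

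**5. The protocol's own counts**

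85,000 / 220,000 = 38.6% and 170,000 / 440,000 = 38.6%. The two shares agree, but neither can be rebuilt from Appendix 4 because no regimen counts are given. In adults, moving the affected regimens between steps 4 and 5 leaves both pooled totals as they are.

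**6. Size, by assumption only**

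Let q be the share of the pooled step 4–5 group on medium- or high-dose ICS plus LTRA or theophylline. Patients whose step depends on this placement = q × pool.

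| q (assumed) | OPCRD, 85,000 | CPRD, 170,000 |
|---|---|---|
| 1% | 850 | 1,700 |
| 5% | 4,250 | 8,500 |
| 10% | 8,500 | 17,000 |
| 20% | 17,000 | 34,000 |

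**The case against.** **The table may be damaged, not wrong.** In its text, rows 2 and 3 end in a dangling *or*, and an *or* is missing inside row 3, so a line may have slipped from row 4 to row 5. This stands as a reason to check the source table. It does not dispose of the point: row 4 does not end in *or*, and the children's conflict survives the shift.

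**Another repair is equally natural.** No row lists medium- or high-dose ICS + LABA + LTRA or THEO, although row 3 lists those triples at low dose. Row 5 may have lost a LABA term, or may be meant to be matched as containing at least the listed drugs. Restoring a LABA term would remove both inversions but leave medium- or high-dose ICS + LTRA or THEO without LABA unassigned. This stands: the documents do not show which repair is right, so the review should not choose one.

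**The consequences are limited.** Severe asthma is defined separately, by ERS/ATS and by the sponsor's trial definition, and neither is said to use Appendix 4. The only stated grouping pools steps 4 and 5. This also stands, except for children.

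**Stronger readings to resist.** A reader might infer that step 5 is mostly LTRA users. No LTRA or theophylline counts appear anywhere. With 1% to 5% of patients at step 5 for other reasons and 0.5% to 3% through these regimens, step 5 would be inflated between (5 + 0.5)/5 = 1.1-fold and (1 + 3)/1 = 4-fold. That range is too wide to support a claim and rests wholly on assumed shares. A reader might also quote a false odds ratio for step 5 between clusters, but the protocol names no model with step 5 as its outcome. Nor does the rank of medium-dose ICS + LTRA above low-dose ICS with three add-ons prove anything. In adults, medium-dose ICS + LABA (4) also ranks above that regimen (3), so counting controllers is not the table's rule.

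**Conclusion.** The point holds in a bounded form. As printed, Appendix 4 orders add-ons one way at low ICS dose and another at medium and high dose. Following it as written misorders a planned severity measure at the boundary between steps 4 and 5. In children it also makes membership of the moderate-to-severe group depend on the add-on.

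The size cannot be determined from the protocol; the patient numbers above are illustrations. The adult pooled step 4–5 group is not affected provided the reconciled table keeps these regimens at step 4 or 5. The ERS/ATS and sponsor-trial definitions are not shown to be affected. The adult part assumes that the row 4/5 boundary is as printed. The children's part assumes that entries without an age label apply to children.

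**What to change.** 1. Check the boundary between rows 4 and 5 against the source table.
2. Reconcile rows 3 to 5 within each age group so that regimens are ordered consistently across ICS doses. State where medium- or high-dose ICS + LABA + LTRA or theophylline falls, and whether a regimen is matched exactly or by the highest entry it contains. Which step is correct is for the sponsor to decide.
3. Rerun the step algorithm before GINA step is tabulated or used as a severity measure in phase 2.
4. Restate the approximate 85,000 and 170,000 only if they were derived from this table and membership changes. They are availability counts, not a powered sample size.

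The cost is one corrected table and one rerun of the algorithm, with no new data.
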